11.3.2 Handling of Missing Data

Cases with missing data for all follow-up CPX at 6, 12 and 24 weeks will be omitted from the efficacy analysis due to inability to calculate the primary endpoint (change in peak VO_2). Considering that the main variable of interest (peak VO_2) is expected not to improve over time with placebo in patients with systolic HF and exclusion of patient with missing

data would inevitably lead to a survivorship bias, we will use the last observation carried forward (LOCF) method to impute the missing data at 12 and 24 weeks for the primary analysis. We will also perform the Little's Missing Completely At Random (MCAR) test to determine whether the appropriateness of imputing missing values and perform a Multivariate Imputation by Chained Equation (MICE) to validate the finding of peak VO₂ using a different method for data inference.

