The recently completed pilot REDHART study, supported by a R34 NHLBI pilot clinical trial grant randomly assigned 60 patients with recently decompensated systolic heart failure to one of 3 strategies: 1) short-term treatment with anakinra for 14 days; 2) longer-term treatment with anakinra for 12 weeks; 3) placebo for 12 weeks. An additional group of eligible patients who declined participation in the study was enrolled in an observational study to evaluate the rate of HF hospitalizations. Anakinra treatment for 12 weeks led to a significant improvement in peak aerobic exercise capacity (peak VO_2), whereas anakinra treatment for 2 weeks did not. No significant changes were seen in placebo. The hospital readmission rate at 6 months was 5% in anakinra 12-week treatment group, 30% in the placebo group, 32% in the anakinra 2-week group, and 35% in the observational group of eligible patients who were not randomized to treatment.

The REDHART2 study is designed to expand and confirm the beneficial effect of sustained anakinra treatment (24 weeks) on peak VO_2 , and to explore the potential effect size on hospital readmissions for HF.

The rationale of Interleukin-1 (IL-1) blockade with anakinra in heart failure stems from the evidence of a) reduced adverse cardiac remodeling and heart failure in animal models of

acute myocardial infarction (AMI); *b*) reduced incidence of heart failure in patients with ST-segment elevation AMI; *c*) enhanced IL-1 activity in patients with heart failure, *d*) quenching of the acute inflammatory response in patients with acute decompensated heart failure, *e*) direct cardiodepressant effects of IL-1 in animal models, *f*) improved exercise capacity in pilot studies including patients with stable systolic heart failure, stable diastolic heart failure, and, recently decompensated systolic heart failure in the pilot REDHART study.

5) OBJECTIVES

The Objective of REDHART2 is to study the effects of IL-1 blockade with anakinra on parameters of aerobic exercise capacity (peak VO₂) at cardiopulmonary exercise test (CPX) after 24 weeks of active treatment, as well as the effects of anakinra on inflammatory biomarkers, structural and functional echocardiographic data, and non-invasive hemodynamics.

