5.1 Primary Endpoint(s)

Placebo-corrected changes in peak VO₂ at CPX after 24 weeks of treatment will be considered the primary endpoint. This will compare patients treated with anakinra (N=68) vs placebo (N=34), and provide a randomized, double-blinded assessment of the effects of IL-1 blockade on aerobic exercise performance. The data will be collected and electronically transferred to the core laboratory at the University of Illinois, Chicago, IL ([name]).

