11.2 Sample Size Considerations

The sample size for this pilot study is calculated according to the primary endpoint of

difference in interval change in peak VO_2 at 24 weeks between anakinra and placebo. Given an expected average peak VO_2 of 15 mL/kg/min for HF patients, 68 subjects randomized to anakinra and 34 subjects randomized to placebo (2:1 randomization) would provide approximately >95% power to detect a difference of 1.6 $\text{mL}\cdot\text{kg}^{-1}\cdot\text{min}^{-1}$ (standard deviation of 1.7-2.0 $\text{mL}\cdot\text{kg}^{-1}\cdot\text{min}^{-1}$) in peak VO_2 on top of placebo. A conservative estimate of 20% loss to follow-up or withdrawal would retain >90% power.

		Effect size of treatment on top of placebo				
	$\text{mL}\cdot\text{kg}^{-1}\cdot\text{min}^{-1}$	+1.2	+1.4	+1.6	+2.4	+3.2
Standard Deviation	2.3	0.70	0.83	0.91	>0.99	>0.99
	2.0	0.82	0.92	0.97†	>0.99	>0.99
	1.7	0.92	0.98	0.99	>0.99	>0.99
	1.4	0.98	0.99	>0.99	>0.99	>0.99*

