11.3 Statistical Analysis

11.3.1 Demographics and Baseline Characteristics

Descriptive summaries of continuous measurements will be reported as median and interquartile ranges due to potential deviation from Gaussian distribution. Descriptive summaries of categorical measurements consist of frequencies, proportions and 95% confidence intervals, when applicable. All analyses will be conducted after database locking once all data has been gathered and electronically captured. All analyses will be based on the intention-to-treat principle (i.e., analyzing groups as randomized and including all patients with outcome data available). The difference in interval changes in peak VO_2 at 24 weeks between the anakinra vs. placebo groups will be compared using random-effect analysis of variance for repeated measures to analyze the effects of treatment within each group and the effect of time_x_group allocation. Unadjusted p-values will be reported throughout, with statistical significance for the primary endpoint set at the 2-tailed 0.050 level. To evaluate the group differences in the secondary endpoints, data will be compared across all groups using the random-effect analysis of variance for repeated measures as indicated above for paired analyses, or Kaplan-Meier curves with Log-rank testing for event rates.

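### Section 11.3.2 sets no rule for death in the week-24 peak VO₂ comparison, and its LOCF rule can carry an on-drug value forward for anakinra stoppers who do not return

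*Combined protocol and SAP*

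**What the plan says.** Section 5.1 defines the endpoint: "Placebo-corrected changes in peak VO₂ at CPX after 24 weeks of treatment will be considered the primary endpoint". Section 11.3.1 claims intention to treat, but limits it to patients who have outcome data.

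Section 11.3.2 then gives two rules.

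- Omission: "Cases with missing data for all follow-up CPX at 6, 12 and 24 weeks will be omitted from the efficacy analysis".
- Imputation: because peak VO₂ is not expected to improve on placebo, and because excluding patients with missing "data would inevitably lead to a survivorship bias, we will use the last observation carried forward (LOCF) method to impute" missing values at weeks 12 and 24 in the primary analysis. MICE is planned as a check.

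Three other places bear on the point.

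- Section 10.2 offers all functional assessments to patients who have stopped treatment, for an intention-to-treat analysis. Its sensitivity analysis over all potential outcomes is for patients whose clinical status cannot be established.
- Section 11.3.1 plans Kaplan-Meier curves and log-rank tests for event rates, separately from peak VO₂.
- Section 11.3.3 closes by saying that all analyses are complete case, which conflicts with LOCF.

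**The concern.** Section 11.3.2 warns against survivorship bias, yet its omission rule removes every patient who dies or leaves before the first follow-up CPX. Its LOCF rule gives a patient who dies after a week-6 or week-12 test the week-24 score of a survivor.

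The defence of LOCF concerns the placebo course only. It does not cover an anakinra patient who was last tested on drug, then stopped and did not come back. Section 4 reports that 12 weeks of anakinra improved peak VO₂ in the pilot, "whereas anakinra treatment for 2 weeks did not". That is not a test of what happens after a longer course is stopped, but it gives no support for assuming that the gain persists.

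At stake is the meaning of the trial's single primary comparison, which section 11.1 offers as the rationale for a phase III trial.

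**Working it through.** **1. The plan's own power figure.** Inputs from section 11.2 are "68 subjects randomized to anakinra and 34 subjects randomized to placebo (2:1 randomization"), a difference of 1.6 mL/kg/min and "standard deviation of 1.7-2.0". Section 11.3.1 gives the test level: "with statistical significance for the primary endpoint set at the 2-tailed 0.050 level". The stated result is that this "would provide approximately >95% power to detect a difference of 1.6".

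Power ≈ Φ(δ / (SD × √(1/68 + 1/34)) − 1.96), where √(1/68 + 1/34) = 0.210.

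- SD 2.0: 1.6 / 0.420 = 3.81, and Φ(1.85) = 0.968. The table says 0.97.
- SD 1.7: 0.994. The table says 0.99.
- After 20% loss (54 v 27), SD 2.0: 0.924, consistent with the stated >90%.

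The sample-size figures are sound. The issue is what the endpoint scores.

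**2. How each type of patient is scored under 11.3.2.**

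| Patient | Week-24 value used |
|---|---|
| Dies or leaves before any follow-up CPX | None; omitted |
| Dies after a week-6 or week-12 CPX | Last value before death |
| Stops treatment, attends week 24 | Observed value (section 10.2) |
| Stops treatment, does not return after an earlier follow-up CPX | Last value, on drug or off drug |

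**3. Non-returning stoppers.** Assumptions, none of them from the documents except the 1.6:

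- a share f of anakinra patients stop and do not return;
- their last CPX was on drug;
- their true week-24 change equals that on placebo;
- nothing is carried forward on placebo that changes its mean.

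The treatment-policy effect is 1.6 × (1 − f). If the carried value holds a fraction c of the gain, LOCF shows 1.6 × (1 − f) + f × c × 1.6.

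| f | True effect | LOCF, c = 1 | Overstatement, c = 1 | c = 0.5 | c = 0.25 |
|---|---|---|---|---|---|
| 10% | 1.44 | 1.60 | 0.16 / 1.44 = 11% | 0.08 / 1.44 = 6% | 0.04 / 1.44 = 3% |
| 20% | 1.28 | 1.60 | 0.32 / 1.28 = 25% | 0.16 / 1.28 = 12.5% | 0.08 / 1.28 = 6% |

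The 20% row borrows the loss allowance in section 11.2, which covers loss of every kind. At SD 2.0 with 68 v 34, power for a true effect of 1.44 is 0.929, and for 1.28 it is 0.861.

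**4. Deaths: direction.** As a crude device to show sign only, score a death as peak VO₂ = 0. That is a change of −15 from the expected mean of 15 in section 11.2. The difference is (1 − pA) × 1.6 − 15 × pA + 15 × pP, where pA and pP are assumed death proportions on anakinra and placebo.

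- 5% in each arm: 1.52.
- 9% anakinra, 3% placebo: 1.456 − 1.35 + 0.45 = 0.56.
- 3% anakinra, 9% placebo: 1.552 − 0.45 + 1.35 = 2.45.

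In this set-up, with deaths left unscored, the figure stays at 1.6 in all three cases.

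**5. Deaths: what each test detects.** Simulation with 68:34, SD 2.0, no effect on peak VO₂, assumed deaths of 15% on anakinra and 3% on placebo, one third of them before week 6. The planned rule has a mean difference near 0 and rejects in about 5% of trials. A rank test with deaths placed worst rejects in about 16%. The separately planned log-rank test rejects in about 43%. With deaths of 10% v 3%, the rank test rejects in only about 8%.

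**The case against.** The strongest reply has four parts.

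**Stoppers are kept in testing.** A reader might infer that all stoppers are scored as if still on drug. Section 10.2 does not support that: those who return contribute observed values. This part stands in full. The problem is limited to non-returners whose last CPX was on drug.

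**Direction and size are not known.** A reader might infer that the rules favour anakinra overall. The documents give no death or discontinuation rates by arm. The only directional evidence, pilot readmission of 5% on 12-week anakinra against 30% on placebo (section 4), points to worse outcomes on placebo; if deaths followed that pattern, leaving them unscored would understate the drug. This stands for deaths. For stoppers, the upward direction holds only if the gain is lost, which the pilot did not test.

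**Deaths are examined elsewhere.** A reader might infer that the trial cannot see excess deaths on anakinra. That is not so: deaths are adjudicated, compared by log-rank and reviewed by the DSMB, and in the scenario above log-rank detects the excess more often than a worst-rank test. What remains is that the peak VO₂ estimate does not reflect them.

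**LOCF may not apply, and MICE is a check.** If the complete-case sentence in 11.3.3 governs, nothing is carried forward. But deaths and non-returners then drop out, and in the model of step 3 the patients left in still show 1.60. MICE has no stated rule for death or for time off drug, so it does not close the gap. The sensitivity analysis in section 10.2 covers unknown status, not known deaths.

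**Conclusion.** The concern holds in limited form. Section 11.3.2 omits patients with no follow-up CPX, early deaths included, against its own warning. If it governs over 11.3.3, it also assigns a week-24 peak VO₂ to patients who have died and to stoppers who do not return.

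For non-returning stoppers the overstatement is at most about 11% or 25% with f of 10% or 20%. That requires the full 1.6 to be carried forward and then wholly lost to the placebo level; it is 6% or 12.5% if half the gain is carried. These are bounds under assumed rates, not expected values.

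For deaths, neither the size nor the sign of the bias can be fixed from the documents. The defect there is a missing definition. The severity is should-fix: the stated power is correct, returning stoppers are handled properly and deaths have their own test, but the primary estimate has no clear meaning for patients who die or disappear.

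**What to change.** Amend sections 11.3.2 and 11.3.3 before database lock.

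1. Make the planned repeated-measures mixed model (or MICE) primary on all randomized patients, using baseline and every observed CPX, including those after treatment was stopped. Keep baseline in the response vector, so that a patient with no follow-up CPX still contributes. Delete the omission rule and the complete-case sentence, and keep LOCF as a sensitivity analysis.
2. State that the primary estimate does not impute a meaningful peak VO₂ after death. Require a supportive rank analysis of week-24 change in which deaths rank below all survivors, ordered by time of death. Its purpose is to make deaths count, not to add power.
3. Add a jump-to-reference MICE sensitivity analysis for anakinra stoppers with no week-24 CPX. The mixed model alone does not settle this case, because it projects non-returners from patients with similar observed values. The analysis needs to know which arm is anakinra, while 11.3.3 gives the analyst only codes A and B. Run it after the code is disclosed, or through an unblinded statistician already on the study.

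The cost is revised wording and a few extra analysis runs on data already collected. The price is a slightly wider and possibly smaller estimate.

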- Section 10.1: We clarified that arthritis is a manifestation of hypersensitivity reaction that can demand discontinuation of the drug.

Prior version dated 08-27-2019 → 10-07-2019

- Section 10.1: Specified the rules for restarting study drug after it has been suspended
- Section 10.2: Distinction between withdrawing treatment and withdrawing from the study and clarification of how long each patient will be followed for safety reasons and how the data will be used after each type of withdrawal
- Section 11.3.2: Clarification of primary method for handling missing data (LOCF)

Temporary Amendment in response to COVID19 Pandemic Emergency 03/27/2020

- Enrollment has been halted on 03/17/2020.
- All patients were instructed to interrupt treatment on that date.
- Follow up provided to assess for any research-related adverse events up to 6 months.
- Adjudication for events after 03/17/2020 will not be completed in consideration of the dynamic changes in the clinical care, challenges in diagnosis ascertainment, and possibility of COVID19 contributing to excess cardiovascular events.

Resuming clinical research operations during COVID19 pandemic change in Protocol version dated 10-07-2019 → 04-24-2020

- Resume screening and enrollment when Governor of Virginia and VCU / VCU Health authorize resumption of elective clinical procedures.
- Change in exclusion criteria, adding a criterion related to COVID19:
 - Evidence of COVID19 within the last 60 days or recent (21 days) exposure to close personal contact. (Section 6.3, bullet 9).

Changes to Key Personnel and DSMB Charter

- [name], has taken on a new position as Associate Director of the Pauley Heart Center and will no longer serve as Regulatory Coordinator for the REDHART2 study; [name] will however serve as DSMB Liaison to the study instead of [name], who has left VCU as June 10, 2020.

- 1) Key Personnel**
- 2) Protocol summary**
- 3) Schematic of study design**
- 4) Description**
- 5) Objectives**
 - 5.1 Primary Endpoint(s)
 - 5.2 Secondary Endpoints
- 6) Enrollment in the study**
 - 6.1 Screening
 - 6.2 Inclusion criteria
 - 6.3 Exclusion criteria
 - 6.4 Alternate consent
- 7) Study design**
 - 7.1 Clinical assessment
 - 7.2 Randomization and allocation concealment
 - 7.3 Investigational treatment
 - 7.4 Cardiopulmonary exercise test
 - 7.5 Echocardiogram
 - 7.6 Non-invasive hemodynamics and bio-impedance
 - 7.7 Questionnaires
 - 7.8 Biomarkers
 - 7.9 Study Schedule
 - 7.14 Cost coverage analysis

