10.2 Handling of Withdrawals

Patients who permanently stop study injection (whether due to adverse event, investigator decision, or patient decision) will be considered withdrawn from treatment. Patients that have withdrawn from treatment will still be offered to complete all the functional assessments to analyze data in an intention-to-treat strategy. Patients who have withdrawn from treatment will also be followed for the complete duration of 6 months follow-up to monitor for safety. Loss to follow-up can occur due to patients' withdrawal or unreported death. If patients are lost to follow up and their clinical condition cannot be established (alive vs dead, hospitalized vs not), they will be excluded from the initial analysis, and then reintroduced for sensitivity analysis considering all potential outcomes.

Patients will be considered withdrawn from study if they express a desire to stop active participation. However, the investigators will continue to record adverse events, hospitalizations, and survival in these patients from the electronic medical record in an observational manner unless these patients withdraw consent. Upon withdrawal of consent, no further information will be collected from those patients.

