11.3.3 Analysis of the Primary Endpoint

The data will be collected and electronically transferred to the core laboratory at the University of Illinois, Chicago, IL, where [name], PhD, will analyze data at the end of the study. After locking the database, he will be provided a group allocation according to treatment A or B (blinded to real treatment). The data will be analyzed according to blinded group allocation and the description of the group allocation will be disclosed only after completion of the analysis. The differences in interval changes between the treatments will be compared using random-effect analysis of variance for repeated measures to analyze the effects of time and group allocation. Unadjusted p values will be reported throughout, with statistical significance set at the 2-tailed 0.05 level. All analyses will be based on a 'complete case' approach.

DSMB CHARTER**Charter, Data and Safety Monitoring Board for**

NHLBI 1R34HL118348-01A1

Interleukin-1 blockade in heart failure with preserved ejection fraction:

REcently Decompensate Heart failure Anakinra Response Trial -2

(REDHART2)

Updated on October 25, 2018

DSMB Liaison: [name] – [contact]

1 Introduction

This Charter is for the Data and Safety Monitoring Board (DSMB) for the study: **Interleukin-1 blockade in recently decompensated heart failure: the REcently Decompensated Heart failure Anakinra Response Trial-2 (REDHART2)**, hereafter referred to as “REDHART2”.

The Charter is intended to be a living document. The DSMB may wish to review it at regular intervals to determine whether any changes in procedure are needed.

2 Responsibilities of the DSMB

The DSMB is responsible for safeguarding the interests of study participants, assessing the safety and efficacy of study procedures, and for monitoring the overall conduct of **REDHART2**.

The DSMB is an independent group advisory to the investigators, and is required to provide recommendations about starting, continuing, and stopping the study **REDHART2**. In addition, the DSMB is asked to make recommendations, as appropriate, to the investigators about:

- Participant safety
- Benefit/risk ratio of procedures and participant burden
- Selection, recruitment, and retention of participants
- Adherence to protocol requirements
- Completeness, quality, and analysis of measurements
- Amendments to the study protocol and consent forms
- Notification of and referral for abnormal findings

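### Sections 11.3.2 (LOCF) and 11.3.3 (complete case) give incompatible rules for missing 24-week peak VO2 in the primary analysis; one must be removed before database lock

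*Combined protocol and SAP*

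**What the plan says.** The primary endpoint is the placebo-corrected change in peak VO2 at 24 weeks (section 5.1), tested two-sided at 0.05 (sections 11.3.1 and 11.3.3). Four places bear on patients without a 24-week value.

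- **Section 11.3.2** sets the inclusion rule: "Cases with missing data for all follow-up CPX at 6, 12 and 24 weeks will be omitted from the efficacy analysis". For everyone else, "we will use the last observation carried forward (LOCF) method to impute the missing data at 12 and 24 weeks for the primary analysis". It gives two reasons. Peak VO2 "is expected not to improve over time with placebo in patients with systolic HF", and excluding patients with missing "data would inevitably lead to a survivorship bias". A multiple-imputation analysis (MICE) is planned to check the result.
- **Section 11.3.3**, headed as the analysis of the primary endpoint, describes the repeated-measures comparison and closes with: "All analyses will be based on a 'complete case' approach". The term is not defined, and nothing calls this a sensitivity analysis.
- **Section 11.3.1** defines intention to treat as analysis by randomized group, "including all patients with outcome data available".
- **The change log**, in the entry for the 10-07-2019 version, lists for section 11.3.2: "Clarification of primary method for handling missing data (LOCF".

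No sentence ranks 11.3.2 above 11.3.3 or the reverse.

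**The concern.** One primary test has two current instructions for the same patients. The section that an analyst would open to run that test directs the exclusion that the section before it rejects as biased. The number analysed, the estimate, its standard error and sometimes the significance verdict depend on which sentence is followed.

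What is at stake is pre-specification. If both rules stand at database lock, either result can be defended from the text. Section 11.3.3 has the analysis run under masked A/B labels, but a two-sided p-value is visible without knowing which label is anakinra, so masking does not settle the choice.

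**Working it through.** **1. Do the two rules differ for any patient?** This is a matter of reading.

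| Patient's follow-up CPX | Section 11.3.2 | Section 11.3.3, ordinary meaning |
|---|---|---|
| 24-week value present | included | included (if only the 24-week value is required) |
| 6- or 12-week value, none at 24 weeks | included, last value carried forward | excluded |
| none at 6, 12 or 24 weeks | omitted | excluded |

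The rules part in the second row. If complete means a value at every visit, they also part for a patient who missed only the 6- or 12-week test. The wording in 11.3.1 fits both rules, because outcome data may mean any follow-up CPX or the 24-week CPX.

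**2. The plan's own power figures (section 11.2).** Inputs: 68 and 34 patients, difference 1.6, SD 1.7 to 2.0, two-sided 0.05, 20% loss or withdrawal.

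- Full sample, SD 2.0: 1.6 / (2.0 × √(1/68 + 1/34)) = 3.81. Power is Φ(3.81 − 1.96) = 0.968, or 0.965 by noncentral t. The table gives 0.97.
- After 20% loss (54 and 27), SD 2.0: 1.6 / (2.0 × √(1/54 + 1/27)) = 3.39. Power is 0.924, or 0.918 by noncentral t. At SD 1.7 the normal approximation gives 0.979.

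The stated figures reproduce. Power above 90% holds for the reduced sample and, with a flat effect, for LOCF too, so it does not show which rule was meant.

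**3. Number analysed.** The share without a 24-week CPX is an assumption. The 20% in section 11.2 is loss or withdrawal, and under section 10.2 "Patients that have withdrawn from treatment will still be offered to complete all the functional assessments", so the share may be lower.

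- 10% missing: complete case 102 × 0.90 ≈ 92; LOCF about 92 to 102.
- 20% missing: complete case 102 × 0.80 ≈ 81-82; LOCF about 82 to 102.

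The LOCF count depends on how many of these patients have an earlier follow-up CPX. At 20%, up to about 20 patients are in or out.

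**4. Same simulated trial analysed under both rules.** Settings: 68:34, SD of change 2.0, random loss (half after week 6, half after week 12), effect constant from week 6, t-test on change, several thousand trials per scenario. If every patient without a 24-week CPX has an earlier one:

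| True effect | Verdict differs, 10% missing | Verdict differs, 20% missing |
|---|---|---|
| 1.6 (design effect) | about 3% | about 6% |
| 1.2 (smallest effect in the power table) | about 8-9% | about 14-15% |
| 0 | about 3% | about 4-5% |

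The median absolute difference between the two estimates is 0.09 at 10% missing and 0.14 at 20%; the 95th percentiles are about 0.28 and 0.42.

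If only half have an earlier CPX, the others are omitted under both rules and cannot cause disagreement. The verdict then differs in about 2% and 4% of trials at effect 1.6, and about 5% and 10% at 1.2.

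**5. Error rate if the choice stays open.** With no effect and all earlier CPX present, LOCF rejects in 5.0% and 5.3% of trials (10% and 20% missing) and complete case in 4.8% and 5.0%. The verdicts differ in 2.7% and 4.4%. The chance that at least one rule gives significance is half the sum of the three: (5.0 + 4.8 + 2.7)/2 ≈ 6.3% and (5.3 + 5.0 + 4.4)/2 ≈ 7.4%. Each rule alone holds about 5%; the excess arises only if the rule is picked after both results are seen.

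**The case against.** The strongest defence is that the documents already point to one rule. Section 11.3.2 names the variable, the visits and the purpose and argues against exclusion, and the change log calls LOCF the primary method. Section 11.3.3 has one generic, undefined sentence. Complete case could loosely mean patients whose endpoint can be calculated, which would agree with the omission rule in 11.3.2. Most of this stands: LOCF is very probably intended and the sentence is probably a leftover. But the loose meaning is neither usual nor stated, and the sentence covers all analyses from within the primary-analysis section. Documented intent makes the correction easy; it does not make the text consistent.

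It is also fair that the upper disagreement figures need every patient without a 24-week CPX to have an earlier one, and use 20% missing, which section 11.2 itself calls conservative. The lower figures are therefore shown beside them.

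Three stronger readings are tempting, and the documents do not support them:

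- **That LOCF is biased here and must be replaced.** With random loss and a flat effect from week 6, LOCF is unbiased. Otherwise the direction depends on the time course between weeks 6 and 24, which the documents do not give. Two invented profiles at 20% missing show this. A build-up of 0.4, 0.8, 1.6 gives 0.1 × 0.4 + 0.1 × 0.8 + 0.8 × 1.6 = 1.40 against a true 1.6. A fade of 1.6, 1.6, 1.2 gives 0.1 × 1.6 + 0.1 × 1.6 + 0.8 × 1.2 = 1.28 against a true 1.2. Neither bears on the contradiction.
- **That LOCF is justified only by what is expected on placebo.** Section 11.3.2 also cites survivorship bias, which is not limited to one arm.
- **That the sample size is wrong.** It reproduces, and the power after loss fits either rule.

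**Conclusion.** The contradiction is real and should be corrected before database lock. It can be seen from the text alone and does not rest on the simulation.

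Its size does rest on assumptions: 10% to 20% without a 24-week CPX, random loss, a constant effect from week 6 and an SD of change of 2.0. On these, the two rules disagree on significance in about 2-6% of trials at the design effect of 1.6 and about 5-15% at 1.2, the range reflecting the share missing and whether half or all of these patients have an earlier CPX. In most simulated trials the conclusion is the same under both rules. The finding is confined to the conflict in wording. It does not show that LOCF is the wrong choice or that the trial is underpowered.

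**What to change.** **Required, before database lock.** Delete the complete-case sentence from section 11.3.3 and refer there to the LOCF rule in section 11.3.2 as the single primary rule. If a complete-case analysis is wanted, define it (24-week CPX present, or all CPX present) and label it a sensitivity analysis beside the planned MICE. The cost is a wording amendment; no new data are needed.

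**Optional.** Fit the planned repeated-measures model by likelihood to all observed peak VO2 values, without single imputation, and report the 24-week contrast. This is valid if data are missing at random. It could be a further sensitivity analysis or, if the sponsor prefers, the primary rule. It would replace a deliberate, amended choice, so it is a preference and is not needed to remove the conflict. It needs minor programming. In the simulations its standard error was slightly larger than under LOCF: about 0.44 against 0.42 at 10% missing, and 0.46 against 0.42 at 20%.

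### Carrying earlier peak VO₂ values forward turns the primary 24-week difference into a mix of week-6, week-12 and week-24 effects

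*Combined protocol and SAP*

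**What the plan says.** Section 5.1 fixes the time point: "Placebo-corrected changes in peak VO₂ at CPX after 24 weeks of treatment will be considered the primary endpoint". Section 11.3.1 names a random-effect repeated-measures analysis of variance "to analyze the effects of treatment within each group and the effect of time_x_group allocation", and section 11.3.3 says that the interval changes will be "compared using random-effect analysis of variance for repeated measures to analyze the effects of time and group allocation". Neither section states a covariance structure, or whether baseline is a visit in the model or is subtracted beforehand.

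On missing values, section 11.3.2 omits only patients with no follow-up exercise test at all. For the rest, "we will use the last observation carried forward (LOCF) method to impute the missing data at 12 and 24 weeks for the primary analysis". It gives two reasons: peak VO₂ is not expected to improve on placebo, and dropping patients with missing tests would bring survivorship bias. It adds Little's test and multiple imputation by chained equations (MICE) as a check. The list of changes at the front of the protocol also calls LOCF the primary method. Section 11.3.3, however, ends by placing all analyses on a complete-case basis, under which nothing would be carried.

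**The concern.** The plan does not say that carried values are flagged, down-weighted or given extra variance. A patient last tested at week 6 therefore contributes a week-6 change under the label of week 24. The placebo rationale does not cover the anakinra arm, where the course of the effect between weeks 6 and 24 is what the trial is meant to learn. If the effect grows or fades over that period, the primary estimate and its interval describe something other than the declared endpoint. Copies also add no within-patient variation, so under one reading of the model the residual variance, and with it the standard error, is too small.

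**Working it through.** **Inputs from the documents.** 68 versus 34 patients, target difference 1.6 mL/kg/min, SD of change 1.7 to 2.0 (2.0 used here), and 20% loss (section 11.2); two-sided 0.05 (section 11.3.1); tests at baseline and weeks 6, 12 and 24. **Assumptions, not in the documents:** when patients are lost, that loss is completely random and equal in both arms, the effects at weeks 6 and 12, and the within-patient correlation.

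**1. The plan's own power.** Section 11.2 claims "approximately >95% power to detect a difference of 1.6" mL/kg/min.
- SE = 2.0 × √(1/68 + 1/34) = 0.420. Power = Φ(1.6/0.420 − 1.96) = 0.968, against 0.97 in the table.
- With 20% lost (54 versus 27), power is 0.924 by the normal formula and 0.918 by the noncentral t. The stated figure above 90% reproduces.

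**2. What the LOCF contrast estimates.** Let p6, p12 and p24 be the shares of analysed patients last seen at each visit, and d6, d12 and d24 the group differences in change at those visits. Then

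LOCF difference = p6·d6 + p12·d12 + p24·d24.

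This does not depend on the covariance structure. With shares 0.1, 0.1 and 0.8:

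| d6 / d12 / d24 | LOCF difference | Week-24 effect |
|---|---|---|
| 0.4 / 0.8 / 1.6 | 0.04 + 0.08 + 1.28 = 1.40 | 1.60 |
| 0.8 / 1.2 / 1.6 | 0.08 + 0.12 + 1.28 = 1.48 | 1.60 |
| 1.6 / 1.6 / 1.6 | 1.60 | 1.60 |
| 1.6 / 1.6 / 0.8 | 0.16 + 0.16 + 0.64 = 0.96 | 0.80 |

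If a third of the 20% is lost before week 6, those patients are omitted and the shares become 0.071, 0.071 and 0.857. The first row is then 0.029 + 0.057 + 1.371 = about 1.46.

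**3. Standard error under a random intercept with baseline as a visit.** In units of the residual variance, the expected within-patient sum of squares over four visits is 3 if complete, 2.5 if week 12 is copied to week 24, and 1.5 if week 6 is copied to weeks 12 and 24. The model SE is multiplied by √(mean/3), and the type I error is 2 × [1 − Φ(1.96 × that factor)].

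| Timing of the 20% loss | Mean/3 | SE factor | Type I error |
|---|---|---|---|
| Half after week 6, half after week 12 | 2.8/3 = 0.933 | 0.966 | 5.8% |
| All after week 6 | 2.7/3 = 0.900 | 0.949 | 6.3% |
| All after week 12 | 2.9/3 = 0.967 | 0.983 | 5.4% |
| One third each: before week 6, after 6, after 12 | 2.857/3 = 0.952 | 0.976 | 5.6% |

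Simulation of the first row with true compound symmetry gave a mean SE of 0.405 against a true sampling SD of 0.417 (ratio 0.97), with type I error 5.8%. At 40% loss the ratio was 0.94 and the type I error 7.2%.

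**4. Standard error under other readings.** Applied to per-patient change scores, which give the same week-24 contrast as an unstructured covariance, LOCF at 20% loss had a ratio of model SE to true SD of 0.98 to 1.01, and type I error of 4.3% to 5.5%. That SE is right for the LOCF quantity.

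**5. Observed visits only.** A random-intercept REML fit without carried values, under compound symmetry and the first-row timing, gave a mean SE of 0.455 (true SD 0.451). With effects 0.8/1.2/1.6 its mean estimate was 1.58 and its power 0.93; LOCF in the same runs gave 1.47.

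**The case against.** - **Whether LOCF applies at all.** Under the closing sentence of section 11.3.3 no value is carried. That conflict stands and must be settled. But section 11.3.2 is explicit about the primary analysis and the list of changes agrees, so LOCF is the more likely intention.
- **Standard error.** A reader might infer that LOCF makes the week-24 standard error too small whatever model is fitted. The documents do not support this: they state no covariance structure, they describe the outcome as a change, and under change scores or an unstructured covariance the SE is calibrated. Nor is the gap between 0.405 and 0.455 an 11% understatement. Only 0.405 versus 0.417 is miscalibration; the rest arises because LOCF estimates a different, less variable quantity.
- **Pilot evidence.** Section 4 reports that "Anakinra treatment for 12 weeks led to a significant improvement in peak aerobic exercise capacity", whereas 2 weeks of treatment did not. A reader might take this as proof of an effect that builds after week 6. It is not: the 2-week arm had stopped drug, and no course from week 6 to week 24 is given. The building effects above are illustrations.
- **Size.** The plan calls its 20% conservative, loss before week 6 produces no carried values, and section 10.2 offers patients who stop treatment all functional assessments. All three reduce the distortion.
- **Survivorship bias.** This is a fair reason not to drop patients. But a likelihood-based model on observed visits keeps every patient with any follow-up test, the same set that section 11.3.2 keeps. It does rely on missing at random, and the simulations, with completely random loss, do not test that.
- **Existing safeguard.** MICE is already planned and deserves credit, but the primary p-value and interval would still come from LOCF.

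**Conclusion.** The point holds for the estimate. Under section 11.3.2 the primary result is a weighted mix of visit effects, and in general it equals the 24-week effect of section 5.1 only if the effect is flat from week 6. In the scenarios computed with a changing effect, the distortion is 0.12 to 0.20 mL/kg/min, downward if the effect builds and upward if it fades; it is zero if the effect is constant. LOCF therefore cannot be defended as reliably conservative. These sizes rest on assumed timing of loss and assumed interim effects.

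The standard-error part is conditional and small. With a random intercept and baseline as a visit, the SE is understated by about 3% (1.7% to 5.1% by timing) and the type I error is 5.4% to 6.3%. Otherwise there is no understatement for the LOCF quantity. The covariance choice matters more: if correlation decays with time, a random-intercept fit to complete data, with no LOCF at all, had type I error of 9.6% to 14% in simulation. Removing LOCF without naming the covariance would leave that larger error in place.

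**What to change.** In section 11.3.2, make the primary analysis a REML repeated-measures model fitted to the observed peak VO₂ at baseline and weeks 6, 12 and 24, with no carried-forward values, an unstructured covariance, and the group difference in change at week 24 as the named contrast. Move LOCF to a sensitivity analysis and keep the planned MICE as a second check. Remove or restrict the complete-case sentence in section 11.3.3 so that both sections give one rule.

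The cost is one or two sentences before database lock, and no new data. At 20% loss the reported SE becomes about 12% wider (0.455/0.405 = 1.12), and the result rests on missing at random. Power at an SD of 2.0 is about 0.93, computed under compound symmetry, against 0.94 for LOCF in the same runs, and remains above the stated 90%.
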